**Table 8–2: ECG abnormality criteria**

Parameter	Age Range	Abnormality Criteria
QT interval (ms)	1m - <12y	≥500
	≥12y	≥500 or ≥60ms increase from Baseline
QTc(F) (ms)	<6m	>490, or >15% increase from Baseline
	6m - <3y	>440, or >15% increase from Baseline
	3y - <12y	>440, or >15% increase from Baseline
	≥12y - <17y	>440, or >15% increase from Baseline
	≥17y	≥500 or ≥60ms increase from Baseline
QTc(B) (ms)	<6m	>490, or >15% increase from Baseline
	6m - <3y	>450, or >15% increase from Baseline
	3y - <12y	>450, or >15% increase from Baseline
	≥12y - <17y	>450, or >15% increase from Baseline
	≥17y	≥500 or ≥60ms increase from Baseline
PR interval (ms)	<6m	>150, or ≥25% increase from Baseline
	6m - <3y	>170, or ≥25% increase from Baseline
	3y - <12y	>180, or ≥25% increase from Baseline

**Table 8–2: ECG abnormality criteria**

Parameter	Age Range	Abnormality Criteria
	≥12y - <17y	>200, or ≥25% increase from Baseline
	≥17y	Treatment-emergent value >200, >220, >250
QRS interval (ms)	<6m	>90, or ≥25% increase from Baseline
	6m - <3y	>90, or ≥25% increase from Baseline
	3y - <12y	>100, or ≥25% increase from Baseline
	≥12y - <17y	≥110, or ≥25% increase from Baseline
	≥17y	Treatment-emergent value ≥100, >120, >140
Heart rate (bpm)	<6m	<100, >180
	6m - <3y	<90, >150
	3y - <12y	<60, >130
	≥12y	<50, >120

Abbreviations: bpm=beats per minute; m=months; ms=milliseconds; QTc=corrected QT interval; y=years. A month is defined as 28 days; a year is defined as 365.25 days.

A subject data listing will be provided that identifies study participants with a clinically significant finding after the first dose of LCM for each type of ECG abnormality.

### 8.4.3 Physical examination

#### 8.4.3.1 Complete physical examination

A complete physical examination will be performed throughout the study, according to the tabular schedule of study procedures.

The complete physical examination will include cardiac and respiratory function via auscultation, temperature measurement, and review of all body systems.

Clinically significant physical examination findings will be reported as AEs.

#### 8.4.3.2 Brief physical examination

A brief physical examination will be performed throughout the study, according to the tabular schedule of study procedures.

The brief physical examination will include a review of the following body systems:

- Cardiovascular
- Pulmonary
- Abdominal (hepato-gastrointestinal)
- Dermatologic

Clinically significant physical examination findings will be reported as AEs.

## **8.4.4 Neurological examination**

### **8.4.4.1 Complete neurological examination**

A complete neurological examination will be performed throughout the study, according to the tabular schedule of study procedures.

The complete neurological examination will include selected assessment of mental status, sensory systems, motor functions, cranial nerves, reflexes, and coordination/cerebellar function.

Clinically significant neurological findings will be reported as AEs.

Summaries of shift from Baseline to Last Visit will be provided based on categories normal, abnormal, not clinically significant, and abnormal, clinically significant. A listing of neurological examination findings from the complete neurological examination will also be provided.

### **8.4.4.2 Brief neurological examination**

A brief neurological examination will be performed throughout the study, according to the tabular schedule of study procedures.

The brief neurological examination will include selected assessment of: mental status, cranial nerves, and coordination/cerebellar function.

Clinically significant neurological findings will be reported as AEs.

A listing of neurological examination findings from the brief neurological examination will also be provided. No summaries of these results are planned.

## **8.4.5 Vagus nerve stimulation**

VNS status is recorded throughout the study, according to the tabular schedule of study procedures, only for those study participants with an implanted VNS device.

A listing of VNS status will be provided only for those study participants with an implanted VNS device.

## **8.4.6 Tanner stage assessment**

Tanner stage will be assessed throughout the study, according to the tabular schedule of study procedures.

The investigator or qualified designee will evaluate the subject's sexual development using the 3-item Tanner scale (ie, for females: breasts, pubic hair, and overall stage; and for males: genitals, pubic hair, and overall stage). The investigator should use clinical judgment in deciding which study participants are selected for evaluation of Tanner Stage (ie, those study participants who are pubescent at screening or those study participants who become pubescent during the course of the study). The investigator will only report the overall score on the Tanner Stage CRF/eCRF module and this will be used for the associated summaries and listings.

A shift table will be produced showing the change in overall Tanner stage (1-5) from Baseline to Last Visit, by gender.

### 8.4.7 Assessment of suicidality

Suicidality will be assessed by trained study personnel using the C-SSRS (Columbia University Medical Center, 2008). This will be completed according to the tabular schedule of study procedures.

For study participants  $\geq 6$  years of age, this scale will be used for screening as well as to assess suicidal ideation and behavior that may occur during the study. All study participants enrolling directly in SP848 and who are  $\geq 6$  years of age will complete the Baseline/Screening version of the C-SSRS at Visit 1 and will complete the Since Last Visit version at subsequent visits. If a subject becomes 6 years of age during the study, the Already Enrolled version of the C-SSRS should be used at the first visit at which the subject is 6 years of age and use the Since Last Visit version at subsequent visits.

The C-SSRS is not validated and will not be used for study participants  $< 6$  years of age. For those study participants, signs and symptoms of depression will be assessed at each visit.

Subject data listings of the data for the C-SSRS will be provided. No summaries of these results are planned.

### 8.4.8 Achenbach Child Behavior Checklist (CBCL)

The Achenbach CBCL will be completed according to the tabular schedule of study procedures, only in countries where a validated translated version is available.

The Achenbach CBCL form is a questionnaire intended to evaluate a child's competencies and behavioral/emotional problems. Depending on the subject's age, 1 of 2 versions of the Achenbach CBCL is used. The CBCL/1½-5 is intended for use in children 18 months to 5 years and 11 months of age. For study participants  $\geq 6$  years to  $\leq 18$  years, the CBCL/6-18 will be used.

The same scale will be completed by the parent(s)/legal representative(s).

The CBCL/1½-5 comprises 100 questions and the CBCL/6-18 comprises 120 questions. In both questionnaires, the occurrence of certain problems and behaviors (in the past 2 months for the CBCL/1½-5 version and in the past 6 months for the CBCL/6-18 version) will be scored on the following scale:

- 0=not true (as far as known)
- 1=somewhat or sometimes true
- 2=very true or often true

The CBCL/1½-5 items will be grouped according to syndrome scales in [Table 8–3](#) and the CBCL/6-18 items will be grouped according to empirically based syndrome scales in [Table 8–4](#). For each syndrome, a raw score will be calculated as the sum of the considered item scores.

**Table 8–3: CBCL/1½-5**

Syndrome scale	Items
Aggressive behavior	8, 15, 16, 18, 20, 27, 29, 35, 40, 42, 44, 53, 58, 66, 69, 81, 85, 88, 96
Anxious/depressed	10, 33, 37, 43, 47, 68, 87, 90

**Table 8–3: CBCL/1½-5**

Syndrome scale	Items
Attention problems	5, 6, 56, 59, 95
Emotionally reactive	21, 46, 51, 79, 82, 83, 92, 97, 99
Sleep problems	22, 38, 48, 64, 74, 84, 94
Somatic complaints	1, 7, 12, 19, 24, 39, 45, 52, 78, 86, 93
Withdrawn	2, 4, 23, 62, 67, 70, 71, 98
Other problems	3, 9, 11, 13, 14, 17, 25, 26, 28, 30, 31, 32, 34, 36, 41, 49, 50, 54, 55, 57, 60, 61, 63, 65, 72, 73, 75, 76, 77, 80, 89, 91, 100

**Table 8–4: CBCL/6-18**

Syndrome scale	Items
Aggressive behavior	3, 16, 19, 20, 21, 22, 23, 37, 57, 68, 86, 87, 88, 89, 94, 95, 97, 104
Anxious/depressed	14, 29, 30, 31, 32, 33, 35, 45, 50, 52, 71, 91, 112
Attention problems	1, 4, 8, 10, 13, 17, 41, 61, 78, 80
Rule-breaking behavior	2, 26, 28, 39, 43, 63, 67, 72, 73, 81, 82, 90, 96, 99, 101, 105, 106
Social problems	11, 12, 25, 27, 34, 36, 38, 48, 62, 64, 79
Somatic complaints	47, 49, 51, 54, 56a, 56b, 56c, 56d, 56e, 56f, 56g
Thought problems	9, 18, 40, 46, 58, 59, 60, 66, 70, 76, 83, 84, 85, 92, 100
Withdrawn/depressed	5, 42, 65, 69, 75, 102, 103, 111

Standardized T-scores are determined for each subject’s raw syndrome and overall scores based on the subject’s age and sex. Tables mapping each raw score to the appropriate T-score are provided in the CBCL Professional Manual. Standardized T-scores determined from each subject’s raw syndrome scale scores will be reproduced programmatically using the spreadsheets “c15group2-probscales18moto5yrs” and “cbcgrou2-probscales6to18”.

Raw scores and change from Baseline for each CBCL/1½-5 syndrome (aggressive behavior, anxious/depressed, attention problems, emotionally reactive, other problems, sleep problems, somatic complaints, and withdrawn) will be summarized for each visit, and Last Visit.

Raw scores and change from Baseline for each CBCL/6-18 syndrome (aggressive behavior, anxious/depressed, attention problems, rule-breaking behavior, social problems, somatic complaints, thought problems, and withdrawn/depressed) will be summarized for each visit, and Last Visit.

The Calculated T-scores, raw scores, and change from Baseline in raw scores will be listed.

A decrease from Baseline (change from Baseline <0) in the CBCL syndrome raw score will indicate improvement in behavior, while an increase (change from Baseline > 0) indicates worsening.

In addition, for both the CBCL/1½-5 syndrome and /6-18 syndrome, subjects will be categorized according to the Calculated T-score as follows:

- T-score is < 65 = “Normal”
- T-score is ≥ 65 = “Borderline or Clinical range (BCR)”

Summaries of shifts from Baseline to each post-Baseline visit, and from Baseline to Last Visit will also be provided based on the CBCL calculated T-score categories of Normal and BCR. The descriptive summaries of change from Baseline and shift summaries will be presented only when a corresponding Baseline value is available.

#### 8.4.9 BRIEF-P and BRIEF assessment

The BRIEF-P/BRIEF assessments will be completed according to the tabular schedule of study procedures, only in countries where a validated translated version is available.

The BRIEF-P and BRIEF are validated tools that will be used for the evaluation of study participants ≥2 to <5 years of age, and ≥5 to ≤18 years of age, respectively.

##### 8.4.9.1 BRIEF-P scores

The BRIEF-P form comprises 63 questions with entry options N (never: scored as 1 point), S (sometimes: scored as 2 points), and O (often: scored as 3 points).

The 63 items are included in the raw Global Executive Composite (GEC) score which ranges from 63 to 189, with higher scores reflecting poorer functioning.

The 3 subscale scores and 5 individual component scores that make up these subscale scores are outlined in [Table 8–5](#).

**Table 8–5: BRIEF-P questionnaire scoring**

Scale/Index	Questions
Inhibit	3, 8, 13, 18, 23, 28, 33, 38, 43, 48, 52, 54, 56, 58, 60, 62
Shift	5, 10, 15, 20, 25, 30, 35, 40, 45, 50
Emotional Control	1, 6, 11, 16, 21, 26, 31, 36, 41, 46
Inhibitory self-control	All from {Inhibit and Emotional Control}
Flexibility	All from {Shift and Emotional Control}
Working Memory	2, 7, 12, 17, 22, 27, 32, 37, 42, 47, 51, 53, 55, 57, 59, 61, 63
Plan/Organize	4, 9, 14, 19, 24, 29, 34, 39, 44, 49

**Table 8–5: BRIEF-P questionnaire scoring**

Scale/Index	Questions
Emergent metacognition	All from {Working Memory and Plan/Organize}
GEC Score	1-63

GEC=Global Executive Composite

Standardized T-scores are determined from each subject’s raw GEC, inhibitory self-control, flexibility, emergent metacognition, and component scores. Tables that map each raw score to the appropriate T-score are provided in the BRIEF-P Professional Manual. Standardized T-scores determined from each subject’s raw GEC score, subscale scores and 5 individual component scores will be produced programmatically using the spreadsheet “briefp-tscores”

T-score values and change from Baseline for the three index scores, the GEC and the 5 individual component scores for the BRIEF-P questionnaire will be summarized for each visit, and Last Visit.

The Calculated T-scores, raw scores, and changes from Baseline in raw scores will be listed.

A decrease from Baseline (change from Baseline <0) in the BRIEF-P syndrome raw score will indicate improvement in behavior, while an increase (change from Baseline > 0) indicates worsening.

In addition, for BRIEF-P, subjects will be categorized according to the Calculated T-score as follows:

- T-score is < 65 = “Normal”
- T-score is ≥ 65 = “Elevated”

Summaries of shifts from Baseline to each post-Baseline visit, and from Baseline to Last Visit will also be provided based on BRIEF-P calculated T-score categories of Normal and Elevated.

The descriptive summaries of change from Baseline and shift summaries will be presented only when a corresponding Baseline value is available.

All BRIEF-P assessment data will be listed.

**8.4.9.2 BRIEF scores**

The BRIEF form comprises 86 questions with entry options N (never: scored as 1 point), S (sometimes: scored as 2 points), and O (often: scored as 3 points).

The first 72 items are included in the GEC score which ranges from 72 to 216, with higher scores reflecting poorer functioning.

The 2 subscale scores and 8 individual component scores that make up these subscale scores are outlined in [Table 8–6](#).

**Table 8–6: BRIEF questionnaire scoring**

Scale/Index	Questions
Inhibit	38, 41, 43, 44, 49, 54, 55, 56, 59, 65

**Table 8–6: BRIEF questionnaire scoring**

Scale/Index	Questions
Shift	5, 6, 8, 12, 13, 23, 30, 39
Emotional Control	1, 7, 20, 25, 26, 45, 50, 62, 64, 70
Behavioral Regulation Index (BRI)	All from {Inhibit, Shift, and Emotional Control}
Initiate	3, 10, 16, 47, 48, 61, 66, 71
Working Memory	2, 9, 17, 19, 24, 27, 32, 33, 37, 57
Plan/Organize	11, 15, 18, 22, 28, 35, 36, 40, 46, 51, 53, 58
Organization of Materials	4, 29, 67, 68, 69, 72
Monitor	14, 21, 31, 34, 42, 52, 60, 63
Metacognition Index (MI)	All from {Initiate, Working Memory, Plan/Organize, Organization of Materials, and Monitor}
GEC Score	1-72

The BRI score is the total of 28 items and ranges from 28-84. The MI score is the total of 44 items and ranges from 44 to 132.

T-score values and change from Baseline for the two indexed scores (BRI and MI), the GEC and the 8 individual component scores for the BRIEF questionnaire will be summarized for each visit, and Last Visit.

Standardized T-scores determined from each subject’s raw GEC score, subscale scores and 8 individual component scores will be produced programmatically using scoring spreadsheet “brief-tscores”. The Standardized T-scores, raw scores, and changes from Baseline in raw scores will be listed.

A decrease from Baseline (change from Baseline <0) in the BRIEF scores indicates improvement, while an increase (change from Baseline > 0) indicates worsening.

In addition, for BRIEF, subjects will be categorized according to the Calculated T-score as follows:

- T-score is < 65 = “Normal”
- T-score is ≥ 65 = “Elevated”

Summaries of shifts from Baseline to each post-Baseline visit, and from Baseline to Last Visit will also be provided based on BRIEF calculated T-score categories of Normal and Elevated.

The descriptive summaries of change from Baseline and shift summaries will be presented only when a corresponding Baseline value is available.

All BRIEF assessment data will be listed.

#### **8.4.10 Bayley-III assessment**

The Bayley-III assessments will be completed according to the tabular schedule of study procedures for study participants <18 months of age at study entry if enrolled in English-speaking countries.

This scale is validated as a tool for assessment of neurological development in young children and is therefore considered appropriate for this study.

The same scale will be completed for children from 1 month to <18 months of age enrolled in English-speaking countries.

The Bayley-III scales are an individually administered adaptive assessment that presents children with situations and tasks designed to produce an observable set of behavioral responses. They consist of a cognitive scale, a language composite scale with receptive and expressive language subscales, and a motor composite scale with fine and gross motor subscales to be completed by the Investigator or designee, and of a social-emotional scale, comprising social emotional competence, and sensory processing, and an adaptive behavior scale, which assesses the attainment of skills necessary for the development of independence, to be completed by the child's parent or caregiver.

The sum of scaled scores entered on the CRF/eCRF module, and the change from Baseline for the scales, as well as the general adaptive composite sum scaled score, will be summarized for each visit, and Last Visit.

All Bayley-III assessment data will be listed.

#### **8.4.11 Medical procedures**

Subjects who had any concomitant medical procedures during the study based on the Concomitant Medical Procedures eCRF module will be listed. Additionally, subjects who had any procedures or surgeries prior to study entry based on the Procedure History CRF/eCRF module will also be listed.

### **8.5 Palatability and ease of use questionnaires**

UCB has created a palatability and ease of use questionnaire to collect data from the subject or caregiver regarding different aspects of LCM and its administration. The questionnaire will assess the subject or caregiver's response regarding the formulation of LCM the subject is receiving for palatability items (eg, taste, smell, ability to swallow, aftertaste), mode of administration, and administration device as applicable.

The number and percentage of study participants who respond to each of the categories presented for the following questionnaires will be summarized at each visit it is assessed:

- Tablet palatability and ease of use
- Oral solution palatability and ease of use

Summaries will be performed overall and by seizure classification group (as defined in Section 3.2.12), with percentages based on the number of study participants with non-missing responses for the specified visit. All palatability and ease of use questionnaire data will be listed.

## 9 PHARMACOKINETICS

All study PK outcomes will be summarized for the PK-PPS.

Blood samples for LCM PK will be completed according to the tabular schedule of study procedures, for the assessment of LCM and concomitant AED plasma concentrations. These blood samples will be collected along with the clinical chemistry/hematology samples at any time after intake of LCM.

### 9.1 Descriptive statistics

Descriptive summaries (n, mean, SD, geometric mean, CV, geometric CV, median, minimum, and maximum) for the LCM plasma concentration and the plasma concentrations for selected concomitant AEDs will be presented by visit, timepoint and actual dose.

## 10 EFFICACY ANALYSES

The study efficacy variables include seizure counts (assessed using seizure diaries in order to evaluate the preliminary efficacy of LCM in this population), the Clinical Global Impression of Change, the Caregiver Global Impression of Change, and quality of life assessments (PedsQL and health care resource use).

All study efficacy variables will be summarized for the FAS, overall and repeated by efficacy seizure classification subgroup (where applicable), using the levels defined in Section 3.2.12. All summaries of efficacy data are descriptive; no statistical testing will be performed.

All efficacy variables will be listed.

### 10.1 Seizure counts

At Screening of SP847 (or other LCM pediatric clinical studies in epilepsy) or at the Screening Visit of SP848 (for study participants who directly enrolled into SP848) study participants/caregivers (including parents/legal guardians) will be asked how many seizures the subject has had in the previous 4 weeks; this will serve as a historical Baseline. After the subject is enrolled in the SP848 study, seizure data will be collected in diaries provided to study participants/caregivers (including parents/legal guardians). Each subject/caregiver (including parent/legal guardian) will keep a diary to note daily seizure activity throughout the current study. The subject/caregiver (including parent/legal guardian) should be reminded to bring the diary with them at each clinic visit. The following information will be recorded:

- Seizure type
- Seizure frequency

Each seizure code in the clinical database will be mapped to exactly 1 of the ILAE seizure codes based on the 1981 ILAE classification (Seizure Count CRF/eCRF module).

Determination of Baseline Period seizures will be made utilizing both the historical Baseline and the seizure diary data collected from the date of the Screening Visit to the day prior to the date of first dose of LCM.

### **10.1.1 Seizure frequency per 28 days**

For study participants with POS, seizure frequency per 28 days (as defined in Section 3.2.13) will be summarized descriptively and presented graphically.

Observed values and change from Baseline during the Titration Period, Post-Titration Period and the overall Treatment Period for the direct enrollers, overall Treatment Period for rollover study and overall Treatment Period for all study participants will be presented.

### **10.1.2 Percent change from Baseline in 28-day partial-onset seizure frequency**

For study participants with POS, descriptive statistics for percent change from Baseline (as defined in Section 3.2.14) in 28-day seizure frequency will be presented. Any subject with seizure data during the time interval will be included in the summary for that seizure time interval.

Descriptive statistics will also be presented for percent change from Baseline in 28-day seizure frequency during the Titration Period, Post-Titration Period and for the overall Treatment Period for direct enrollers, for the overall Treatment Period for the rollover study participants and for the overall Treatment Period for all study participants.

Descriptive statistics for percent change from Baseline in 28-day seizure frequency during the Treatment Period will also be presented by seizure type (simple partial, complex partial, secondarily generalized) for POS. Only study participants who experienced a seizure type during the Baseline Period will be included in the analysis for that seizure type with only the seizure frequencies of that seizure type being used in the analysis.

Descriptive statistics for percent change from Baseline to each time interval in 28-day seizure frequency during the Treatment Period will also be presented. Any subject with seizure data during the time interval will be included in the summary for that seizure time interval and by seizure type.

The percent change from Baseline in 28-day seizure frequency among completer cohorts (as defined in Section 3.2.19) will also be presented.

### **10.1.3 $\geq 50\%$ reduction in 28-days partial-onset seizure frequency**

For study participants with POS, the number and percentage with  $\geq 50\%$  reduction in 28-day partial-onset seizure frequency ( $\geq 50\%$  responders) will be summarized by seizure time intervals (as defined in Section 3.2.21) and by seizure type (simple partial, complex partial, secondarily generalized). Any subject with seizure data during the time interval will be included in the summary for that seizure time interval and by seizure type.

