### **3.2.15 Response to treatment**

Response to treatment is based on the percent change in seizure frequency relative to Baseline (using the Baseline definition in Section 3.3). Study participants who experience at least a 50% reduction from Baseline will be considered  $\geq 50\%$  responders. Study participants who experience at least a 75% reduction from Baseline will be considered  $\geq 75\%$  responders.

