#### **3.5.3 Full Analysis Set**

The Full Analysis Set (FAS) will be used for the analysis of seizure data and will consist of all study participants in the SS, who have at least 1 completed post-Baseline seizure diary.

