### **10.1.4 $\geq 75\%$ reduction in 28-days partial-onset seizure frequency**

The analyses described in Section 10.1.3 for  $\geq 50\%$  reduction in 28-days partial-onset seizure frequency will also be performed for study participants with  $\geq 75\%$  reduction in 28-day partial-onset seizure frequency ( $\geq 75\%$  responders).

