### 10.1.6 Seizure-free status

The number and percentage of study participants achieving a seizure-free status (as defined in Section 3.2.18) will be presented for overall treatment period. This will be presented by completer cohorts (as defined in Section 3.2.19).

The number and percentage of study participants seizure-free among completer cohorts (as defined in Section 3.2.19) will also be presented separately by seizure type (simple partial, complex partial, secondarily generalized) for subjects with POS.

Seizure-free status will also be presented by seizure time intervals (as defined in Section 3.2.21). The number and percentage of study participants with seizure-free status at the end of each time interval during the treatment period will be presented separately by seizure type (simple partial, complex partial, secondarily generalized) for POS.

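### By-seizure-type responder and seizure-free tables lack the Baseline-type restriction used for percent change, so their denominators are unsettled and by-type seizure freedom can be inflated

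*SAP*

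**What the plan says.** The SAP uses different populations for its by-type seizure analyses (simple partial, complex partial, secondarily generalized).

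- **Section 10.1.2, percent change over the Treatment Period by type:** "Only study participants who experienced a seizure type during the Baseline Period will be included in the analysis for that seizure type", using only that type's frequencies.
- **Section 10.1.2, percent change by time interval:** the next paragraph drops this limit and uses the same open sentence as Section 10.1.3.
- **Section 10.1.3, 50% responders:** "Any subject with seizure data during the time interval will be included in the summary for that seizure time interval and by seizure type". No Baseline condition is attached.
- **Section 10.1.4, 75% responders:** repeats the 10.1.3 analyses, so the open rule carries over.
- **Section 10.1.6, seizure-free status:** the completer-cohort counts "will also be presented separately by seizure type (simple partial, complex partial, secondarily generalized) for subjects with POS". For time intervals, "The number and percentage of study participants with seizure-free status at the end of each time interval during the treatment period will be presented" by type, again for POS only. Neither statement requires the type at Baseline.

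Four definitions bear on this. Section 3.2.15 states that "Response to treatment is based on the percent change in seizure frequency relative to Baseline". Section 3.2.14 divides that change by the Baseline frequency. Section 3.2.18 defines seizure-free as no seizures in a completed period with at most 10% of diary days missing, and has no version for a single type. Section 3.5.3 admits to the Full Analysis Set members of the Safety Set "who have at least 1 completed post-Baseline seizure diary", with no Baseline requirement.

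**The concern.** A zero Baseline for a given type is to be expected in this design. Section 3.2.12 makes a participant POS after any Type I seizure in the classification history, and Section 6.3.1 takes that history from any time before study entry. Baseline seizure counts come from a 4-week recall, combined with diary days before the first dose (Sections 6.3.3 and 10.1). Nothing requires a participant to have had all three subtypes, or any partial-onset seizure in that short window.

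Such a participant cannot improve on a type that was absent at Baseline. In a by-type seizure-free table the participant may nevertheless count as a success. In a by-type responder table the participant has no defined outcome, yet the inclusion sentence says to include everyone with data. A reader could take a high seizure-free rate for a type as a treatment result when part of it reflects how uncommon the type is. Nor could the reader reconcile that table with the by-type percent-change table, which uses a different population.

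**Working it through.** The SAP states no rate, prevalence or count on this point, so there is no figure to reproduce. The check applies the SAP's formulas to a zero Baseline and then works through assumed values.

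**Step 1. Percent change at zero Baseline.** Section 3.2.14: PCH = [(SF_T − SF_B)/SF_B] × 100.

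- SF_B = 4, SF_T = 1: (1 − 4)/4 × 100 = −75%, a responder at both thresholds.
- SF_B = 0, SF_T = 0: undefined.
- SF_B = 0, SF_T = 3: undefined.

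Section 3.2.15 therefore assigns no responder status to a participant without the type at Baseline.

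**Step 2. Inputs, all assumed.**

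- b, share of POS participants with the type at Baseline: 0.3 to 0.9.
- r, responder rate among those with the type: 0.5.
- s, share of those with the type who become free of it: 0.1 to 0.3.
- t, share of those without the type who stay free of it: 0.8 to 1.0.

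**Step 3. By-type responders.** With the 10.1.2 restriction the rate is r. If everyone with diary data stays in the denominator and zero-Baseline participants count as non-responders, it is b × r. If undefined values are dropped, it is r again.

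| b | restricted, or undefined dropped | all kept in denominator |
|---|---|---|
| 0.3 | 50% | 0.3 × 0.5 = 15% |
| 0.5 | 50% | 0.5 × 0.5 = 25% |
| 0.7 | 50% | 0.7 × 0.5 = 35% |
| 0.9 | 50% | 0.9 × 0.5 = 45% |

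**Step 4. By-type seizure freedom, read as no seizures of that type.** Restricted rate: s. Unrestricted rate: b × s + (1 − b) × t, which equals s + (1 − b)(t − s). It exceeds s whenever t is greater than s. With s = 20% and t = 90%:

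| b | restricted | unrestricted |
|---|---|---|
| 0.3 | 20% | 0.06 + 0.63 = 69% |
| 0.5 | 20% | 0.10 + 0.45 = 55% |
| 0.7 | 20% | 0.14 + 0.27 = 41% |
| 0.9 | 20% | 0.18 + 0.09 = 27% |

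Across the full assumed range the unrestricted rate runs from 0.9 × 0.1 + 0.1 × 0.8 = 17% to 0.3 × 0.3 + 0.7 × 1.0 = 79%, against 10% to 30% among those with the type.

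**Step 5. By-interval percent change.** An undefined value cannot enter a mean or median, so the open sentence in 10.1.2 does not itself move those statistics. It does contradict the paragraph before it and leaves the reported n unclear.

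**The case against.** A reader might infer that the SAP dilutes by-type responder rates. The text does not establish this. Section 4.2.1 plans no imputation and uses only reported data, and Section 3.1 bases denominators on the participants appropriate to each analysis. Dropping an undefined percent change fits both and leaves the rate unchanged. The same open sentence also governs percent change by interval in 10.1.2, where undefined values cannot be used, so it may be meant only to say that data in the interval suffice. This objection stands: dilution is one of two readings. What remains is that the literal instruction to include everyone with data points the other way, and the SAP does not choose.

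A reader might also take inflated seizure freedom as certain. Section 3.2.18 defines freedom from all seizures. If that definition applies in 10.1.6, seizure type only groups participants and the mechanism in Step 4 does not operate. Freedom from the named type is the more natural reading of those tables, but it is not written down. The inflation is therefore conditional, and the missing definition is part of the problem.

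Finally, it is tempting to say that the secondary efficacy variables are compromised. Section 2.3.4.3 describes the secondary analyses as covering the overall Treatment Period and lists presentations by type and by interval among the other efficacy variables. Nothing is tested, no primary efficacy variable exists, and the overall seizure-free count in 10.1.6 is untouched by the by-type issue. This limits the importance. It does not remove the inconsistency, because Sections 10.1.3 and 10.1.6 commit to producing the by-type tables.

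**Conclusion.** The point holds as an inconsistency that should be fixed. The SAP states the appropriate by-type population once, in 10.1.2, and does not carry it into the by-interval paragraph of that section or into 10.1.3, 10.1.4 and 10.1.6.

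- **Seizure freedom by type:** inflated if it means no seizures of that type and participants without the type mostly stay free of it. The excess is (1 − b)(t − s): 35 percentage points in the central illustration (0.5 × 0.7) and 7 points at 90% prevalence (0.1 × 0.7). These sizes rest entirely on assumed values, so the document does not support saying that the tables mainly measure type prevalence.
- **Response by type:** indeterminate rather than shown to be diluted. The text allows both 25% and 50% in the same illustration.
- **Response across all partial-onset seizures:** the same zero-Baseline question arises, because the Full Analysis Set requires no Baseline frequency. Its extent cannot be judged from the SAP.

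The consequence is for the interpretation of descriptive tables.

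**What to change.** 1. Apply the Baseline-type restriction of 10.1.2 to numerator and denominator in 10.1.3, 10.1.4 and the by-type parts of 10.1.6, and to the by-interval paragraph of 10.1.2.
2. Define by-type seizure freedom as no seizures of that type in the period, under the completion and diary conditions of Section 3.2.18.
3. Restrict the responder tables for all partial-onset seizures to participants with a Baseline partial-onset frequency above 0, and state that a zero or missing Baseline gives no responder status.
4. Show n for each type. Report participants excluded for lack of the type at Baseline, and new onset of a type during treatment, as separate counts so that neither is lost.

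The cost is a few sentences of SAP text and a programming filter based on a rule the SAP already contains. The price is smaller by-type denominators, and hence less precise percentages for uncommon types.
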